2.1. Study Population (Cases)

Protocol FMSU2017-002B will include an enriched sample of 300 cases obtained from multiple image acquisition centers on protocol FMSU2013-004A. As part of the consent process for protocol FMSU2013-004A subjects agreed that image data and supporting documentation could be used for future research and investigations. All cases for this pivotal MRMC reader study will meet the following eligibility inclusion and exclusion criteria:

Inclusion Criteria

• Eligible subjects under protocol FMSU2013-004A, defined as female subjects with known true clinical status and with complete FFDM and DBT examinations, in which

there is sufficient anatomical coverage, sufficient contrast, and no significant motion or other artifacts, as determined by the image-acquisition sites.

• Meet none of the exclusion criteria under protocol FMSU2013-004A.

Exclusion Criteria

- Subjects who are in violation of protocol FMSU2013-004A.
- Subjects who meet exclusion criteria under Fujifilm protocol FMSU2013-004A.
- Subjects with unknown clinical status.
- Any subject whose positive mammogram was not read during the truthing process will not be considered for the pivotal reader study.

Case selection. The study sample was selected by BCL per the approved "Case Selection Specifications for FUJIFILM Medical Systems U.S.A., Inc. protocol FMSU2017-002B: A Multi-Reader Multi-Case Controlled Clinical Trial to Evaluate the Comparative Accuracy of Fujifilm DBT plus S-View versus FFDM Alone in the Detection of Breast Cancer – A Pivotal Study (Revision 1)", dated and approved 7 March 2018. Cases were selected from subjects with images acquired in the N-Mode dose setting, as specified in the Indications for Use for the ASPIRE Cristalle Digital Breast Tomosynthesis Option (P160031). Cases were selected based on levels of the following factors: 1) Reference standard status, 2) Presence of calcifications (yes or no), 3) Breast composition (density), and to the extent possible given the pool of available cases, 4) Acquisition site. Backup cases to be used in the event that selected cases were not available (for example, image files become corrupted) also were identified, matched as closely as possible to the values of the selection factors for each selected case. Images from all cases used on the pivotal study will have passed quality control review by the Fujifilm team.

Demographic and clinical characteristics. Demographic and clinical characteristics were obtained on Fujifilm protocol FMSU2013-004A (see **Appendix 1** for relevant form pages). The sample includes 60 cancer cases and 240 non-cancer cases comprised of 48 benign cases, 72 recall cases, and 120 normal cases. Cases without biopsy are from the screening or recall enrollment pathways and have one-year negative imaging follow-up.

2.2. Study Radiologists (Readers)

Approximately 18 radiologists will participate as study readers. Readers may be radiologists of varying experience levels, from both community and academic practices, some of whom have

limited experience reading 2D synthetic images. Reader information is recorded on a dedicated two-part (2-part) questionnaire (**Appendix 1**).

Qualifications. All readers must be board-certified and Mammography Quality Standards Act (MQSA)-qualified for both FFDM and DBT interpretation.

Training. Readers will receive approximately three (3) hours of training in the evaluation of DBT plus S-View images. Training will also consist of a hands-on session at the workstation to provide the readers with an overview of its DBT-specific functionality. For each view, mediolateral oblique (MLO) and craniocaudal (CC) 2D FFDM and the corresponding S-View image for the same view will be shown with the DBT images. The training will also emphasize that the S-View images alone will not be used for diagnosis, and scoring will be based on the appearance of the lesion on the DBT images.

3. Test Methods

3.1. Reference Standard

The reference standard for cancer and benign cases is biopsy proof. The reference standard for recall and normal cases is one-year follow-up imaging (320 to 455 days inclusive). The truthers' lesion type(s) and location(s) for all cancer cases in both modalities (FFDM and DBT plus S-View) will be recorded on an electronic case report form (eCRF; **Appendix 1**).

3.2. Randomization

Randomization was performed by BCL per the approved "Randomization Specifications for FUJIFILM Medical Systems U.S.A., Inc. protocol FMSU2017-002B: A Multi-Reader Multi-Case Controlled Clinical Trial to Evaluate the Comparative Accuracy of Fujifilm DBT plus S-View versus FFDM Alone in the Detection of Breast Cancer – A Pivotal Study," dated and approved 09 March 2018.

The 300 cases were randomly allocated into four (4) sets of 75 cases each, case subsets A, B, C, and D, each with 15 cancer cases, 12 benign cases, 18 recall cases, and 30 normal cases. Allocation was balanced to the extent possible on presence of calcifications, breast composition (fatty or dense), and image acquisition site using optimal nonbipartite random matching.² Each Session will comprise three (3) days of reading; we refer to the first part of the Session as Part 1, and the remainder as Part 2.

We used the principle of Latin squares to reduce bias associated with reading order.³ This was achieved by counterbalancing case sets and reading condition (FFDM, DBT plus S-View) in the four portions of each Session (Part 1 Group 1, Part 1 Group 2, Part 2 Group 1, Part 2 Group 2) to ensure that:

- Interpretation within each Part of the Session is half FFDM, half DBT plus S-View (that is, we place this constraint on the study design);
- Each Session uses all four (4) case sets A, B, C, D;
- Each case set is interpreted once as FFDM and once as DBT plus S-View, on separate Sessions;
- Each of FFDM, DBT plus S-View is interpreted at a different Part and Group combination between Sessions; and
- Each case set is interpreted at a different Part and Group combination between Sessions.

Reading order was randomly determined for each reader. The Wald-Wolfowitz runs test⁴, at statistical significance level alpha = 0.05, was used to ensure that for each reader the null hypothesis that the distribution of cancer cases in the list is random was not rejected in favor of the two-sided alternative hypothesis that this distribution is not random.

3.3. Image Review Procedures

Study readings are scheduled to occur at International HealthCare, LLC (Norwalk, CT) between 6 April 2018 and 24 May 2018. Each reader will read both FFDM and DBT plus S-View images for each case, separated by a memory washout period, on the ASPIRE Bellus II workstation.

3.4. Image Interpretation Results

Readers will be prompted by scribes, who will enter each reader's responses in the reader eCRF (**Appendix 1**). For each case on each read, the reader will first note whether there are mammographic findings. If the answer to this question is "no" the reader will be asked to provide a BI-RADS assessment category of 1 or 2, a probability of malignancy (POM) score in 0% through 100%, and a recall decision of "no." If the reader answers "yes" to whether there are mammographic findings the reader will be asked to confirm an initial BI-RADS assessment

category of 0, and will then provide detailed information for up to three (3) suspicious findings (reader lesions):

- Location (including breast [right or left], diagram location [1 9 or combinations when the finding is in multiple diagram sections] within view [right CC, left CC, right MLO, left MLO], and coordinates for each of CC and MLO [N/A if not seen on that view; or X, Y, and for DBT only, Slice])
- Type, as mass, asymmetry, calcification, architectural distortion, or other with description. The reader may check all that apply.
- Forced BI-RADS assessment category 1, 2, 3, 4, or 5
- POM in 0% through 100%

The reader will then be asked for her or his overall recall decision (yes or no), forced BI-RADS assessment category, and POM score, for the case.

In cases with mammographic findings, consistency of BI-RADS scores, POM scores, and recall decisions will not be forced – for example, readers will be permitted to use the full range of POM scores for a finding no matter what BI-RADS score they assign to it.

3.5. Lesion Matching (Scoring)

An expert not associated with diagnosing cases at the image acquisition sites or serving as a study reader will perform lesion matching to determine whether the location and type of any reader findings match a lesion annotated by the truther. Lesion matching will be performed for all malignant lesions in cancer cases. The lesion matcher's results will be recorded on an eCRF (**Appendix 1**).

3.6. Blinding / Masking

The readers will be told that the samples of cases do not represent a standard screening population, and will be blinded to the actual distribution and nature of the set of images they will be asked to review. Readers will be masked to the reference standard and image acquisition interpretations (under Fujifilm protocol FMSU2013-004A) for each case. Readers will not have access to prior mammograms or other clinical information. All readers will perform their interpretations independently.

4. Statistical Methods

Informed consent. By approving this SAP, Fujifilm confirms the following: All subjects whose images were acquired under FMSU2013-004A and selected for this study were consented. As part of the consent process, subjects agreed that image data and supporting documentation could be used for future research and investigations. Each reader will be consented before initiating the reader study.

Masking to protect identities. Study case identification numbers and study reader numbers will be assigned to all cases and readers, and used to protect their identities in statistical analysis and in reporting of results.

Statistician not blinded. Because the reader data on lesion locations only includes Slice for DBT, the statistician will not be blinded to reading condition.

General conventions: Descriptive summaries. Baseline descriptive summaries will include the distribution of demographic characteristics and clinical characteristics, including characteristics specific to malignant and, if appropriate, benign lesions. We also will provide summaries across readers of the per-subject number of findings, BI-RADS scores, POM scores, and per-subject recall scores, for the FFDM and DBT plus S-View readings. These may be crossclassified by, for example, presence of malignant lesions. Categorical variables (such as cancer type and breast tissue composition) generally will be summarized using frequencies and proportions or percentages, while continuous variables generally will be summarized using means and standard deviations (SDs), and/or medians and quartiles or ranges. Missing values generally will be reported as such in these descriptive summaries.

General conventions: Statistical inferences. Uncertainty in estimates of diagnostic accuracy will be quantified through confidence intervals (CIs). Unless otherwise noted, statistical inference procedures (hypothesis tests, CIs) are two-sided with significance level alpha = 0.05 and corresponding confidence level 0.95. Statistical inferences for proportions (for example, sensitivity and specificity) may use the binomial distribution or other exact methods rather than normal approximations, for example, when sample sizes are small and/or when proportions are close to zero or one. Results will be presented by reader using reader numbers to mask reader identities, and averaged across readers.

4.1. Study Samples (Analysis Sets)

Intent-to-diagnose population. The intent-to-diagnose population comprises each reader's interpretation of each study case in each modality (FFDM, DBT plus S-View).⁵ Missing interpretations are not anticipated; in the event that any interpretations are missing in the study database they will be accounted for when reporting study results. We plan to include all readers' interpretations of all cases in both modalities in the analysis set.

If any protocol deviations or violations are reported to the statistician, the statistician will evaluate them to determine their impact on the integrity of the study database, and will determine whether any affected data points should be excluded from primary analysis (that is, whether primary analysis should occur in a modified intent-to-diagnose population).

Unit of analysis. The primary unit of analysis on this study is the subject (case). Malignant lesion is the secondary unit of analysis for per-lesion sensitivity.

4.2. Treatment Assignment

This is a retrospective study for which imaging and clinical management occurred prior to case selection. All cases will be evaluated the same way by all study readers, such that there are no treatment assignments or treatment groups.

4.3. Multiple Centers (Pooling)

Fujifilm obtained images from multiple centers. The protocol for data submission, quality review passed by all images, and reference standard status determination for all images used in the pivotal MRMC study were common. Cases will be pooled across enrolling centers for interpretation on the pivotal MRMC study using common interpretation protocol and eCRFs, and results of interpretation sessions will be monitored. The scoring of (lesion matching for) reader interpretations will follow a common process. Results for any particular reader therefore will be pooled across enrolling centers.

4.4. Derived Variables

Per-subject BI-RADS, POM, and recall scores requiring correct lesion localization will be derived as shown below. The general principle is that even at the subject level, credit is only given for identifying a subject with cancer if the reader marks findings in at least one location

with cancer. Findings that do not match the location of a malignant lesion are ignored for cancer cases in the per-subject analyses but may be reported, generally in an appendix.

Per-Subject scoring: POM and BI-RADS. The primary endpoint is per-subject AUC based on POM scores requiring correct lesion localization. Secondary endpoints include per-subject sensitivity requiring correct lesion localization and specificity based on BI-RADS categories. When computing sensitivity and specificity based on BI-RADS, a score of 4 or 5 constitutes a positive test result. A cutoff score of BI-RADS 3 or higher may also be used to compute the sensitivity and specificity in secondary analyses. Scores for use in these analyses will be derived by the statistician as summarized in **Table 1** on page 15.

Per-Subject scoring: Recall. Secondary endpoints include per-subject recall rate for non-cancer cases and separately for cancer cases requiring correct lesion localization, based on a separate yes/no question. Scores for use in this per-subject analysis will be derived by the statistician as summarized in **Table 2**.

True Positive, False Negative, True Negative, and False Positive. In per-subject analysis of sensitivity and specificity:

- A true positive (TP) occurs when a case contains one or more cancerous lesions and the per-subject BI-RADS score requiring correct lesion localization is 4 or 5.
- A false negative (FN) occurs when a case contains one or more cancerous lesions and the per-subject BI-RADS score requiring correct lesion localization is 1, 2, or 3.
- A true negative (TN) occurs when a case does not have any cancerous lesions and the per-subject BI-RADS score is 1, 2, or 3.
- A false positive (FP) occurs when a case does not have any cancerous lesions and the persubject BI-RADS score is 4 or 5.

A cutoff score of BI-RADS 3 or higher may also be used to compute the sensitivity and specificity in secondary analyses. When computing recall rates requiring correct lesion localization, a *recall* occurs when a case has per-subject recall score equal to yes.

Reference standard	Reader's interpretation	Per-Subject POM and BI-RADS
No malignancies in this case	No findings in this case	 POM: Same as POM recorded by the reader for the case. BI-RADS: Same as BI-RADS category recorded by the reader for the case. From Initial Mammographic Findings form page.
	One or more findings in this case	 POM: Overall POM recorded by the reader for the case. BI-RADS: Overall BI-RADS category recorded by the reader for the case. From Overall Patient Recall form page.
One or more malignancies in this case ^{1,2}	No findings in this case	 POM: Same as POM recorded by the reader for the case. BI-RADS: Same as BI-RADS category recorded by the reader for the case. From Initial Mammographic Findings form page.
	Findings in this case, but no findings matching the location(s) of any proven malignancies in this case	POM: Assigned as the higher of 0 or, for readers who do not assign POM 0 to any case in a reading modality, the minimum POM score assigned by that reader in that modality. BI-RADS: Assigned as category one (1).
	One or more findings correctly matching the location(s) of any proven malignancies in this case	 POM: Highest POM score recorded by the reader for any of these matched findings. BI-RADS: Highest BI-RADS category recorded by the reader for any of these matched findings.

Table 1. Per-Subject POM and BI-RADS Scores Requiring Correct Lesion Localization

¹If the case contains more than one malignant lesion, the reader will get credit for identifying the case as having one or more proven malignancies even if the reader does not identify all of the proven malignancies in the case. For example in a bilateral case, the reader would get credit for identifying the case even if the reader marks findings in only one breast.

²The POM scores and BI-RADS categories for any reader findings in this case that do not match the location(s) of any proven malignancies will be ignored in the per-subject analysis, which requires a single POM score and single BI- RADS category per subject conditional on whether the subject does or does not have proven malignancies.

Reference standard	Reader's interpretation	Per-Subject Recall Score
No malignancies in this case	No recall (initially or overall)	Same as recall recorded by the reader for the case, that is, no recall.
	Recall (initially and overall)	Same as recall recorded by the reader for the case, that is, recall.
One or more malignancies in	No recall (initially or overall)	Same as recall recorded by the reader for the case, that is, no recall.
this case ¹	Recall (initially and overall) and Findings in this case, but no findings matching the location(s) of any proven malignancies in this case	Assigned as no recall.
	Recall (initially and overall) and One or more findings correctly matching the location(s) of any proven malignancies in this case	Same as recall recorded by the reader for the case, that is, recall.
¹ If the case contains more than one malignant lesion, the reader will get credit for recalling the case		

Table 2. Per-Subject Recall Scores Requiring Correct Lesion Localization

¹If the case contains more than one malignant lesion, the reader will get credit for recalling the case even if the reader does not identify all of the proven malignancies in the case. For example in a bilateral case, the reader would get credit for recalling the case even if the reader marks findings in only one breast as long as the overall decision is to recall the subject.

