12.3.1 Per-subject scoring: POM and BI-RADS

The primary endpoint is per-subject AUC based on POM scores requiring correct lesion localization. Secondary endpoints include per-subject sensitivity and specificity based on BI-RADS categories. When computing sensitivity and specificity based on BI-RADS, a score of 4 or 5 constitutes a positive test result. A cutoff score of BI-RADS 3 or higher may also be used to compute the sensitivity and specificity in secondary analyses. Scores for use in these per-subject analyses will be derived by the statistician as described below and summarized in Table 6:

- If a case has no proven malignancies:
 - If the reader does not record any findings in this case: The POM score for this case will be the same as the POM score recorded by the reader for the case, and the BI-RADS score for this case will be the same as the BI-RADS assessment category recorded by the reader for the case.
 - If the reader records any findings in this case: The overall POM score recorded by the reader for the case, and the overall BI-RADS category recorded by the reader for the case will be used, after describing those findings.
- If a case has one or more proven malignancies:
 - If the reader records one or more findings that are determined by the truther to match the location(s) of **any** proven malignancies in this case: The maximum of the POM scores recorded by the reader for those findings will be assigned to the case, and the BI-RADS category for the case will be assigned as the maximum of the BI-RADS categories recorded by the reader for those findings.
 - If the case contains more than one malignant lesion, the reader will get credit for identifying the case as having one or more proven malignancies even if the reader does not identify all of the proven malignancies in the case. For example in a bilateral case, the reader would get credit for identifying the case even if the reader marks findings in only one breast.
 - If the reader does not record any findings in this case; or when the reader records findings in this case, but none of them are determined by the lesion matcher to match the location(s) of any proven malignancies:
 - If the reader did not record any findings in the case, the POM score for this case will be the same as the POM score recorded by the reader for the case and the BI-RADS score for this case will be the same as the BI-RADS assessment category recorded by the reader for the case

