4.11. Data Quality Review

Study database. Data for truthing, readings, and lesion matching on pivotal protocol FMSU2017-002B will be provided to BCL following approved data transfer specifications, to be developed by Fujifilm's study data vendor (Prosoft Clinical, Wayne, PA). *Analysis data: Subject level* will be derived from a subset of protocol FMSU2013-004A *Analysis data: Subject level* in the archive generated by BCL for that study. Fujifilm will transfer reader experience data directly to BCL in comma-separated values (CSV) format.

Review and queries. BCL will examine the database for complete data and, if any data points are missing, query Fujifilm regarding reasons for this missingness. BCL also will verify that data values fall in allowable ranges and follow logical flow, and query Fujifilm regarding any exceptions. Fujifilm will resolve any such issues in the database, and provide responses and an updated database to the statistician. BCL will review the replies and updated database, and declare the data "all clean" if BCL determines that all queries have been resolved sufficiently for analysis to proceed. If data are not "all clean", BCL will query any remaining exceptions and Fujifilm will reply as above. Data will be locked only after BCL declares the database all clean.

BCL will use this final study database for all final study analysis. Final study analysis may be delayed until the study database is locked.

Missing Responses, Indeterminate Results, and Outliers. BCL will review the reasons for any missing data to evaluate whether the missingness is most likely missing completely at random, missing at random, or systematic. BCL will determine appropriate methods for handling the missing data based on this evaluation and the amount of missingness. If BCL needs to amend this SAP to include more details for handling missing data, we will add these details before carrying out the analysis. In particular, if statistical models are used to address missing data issues these models and their assumptions will be explained clearly, and robustness of results will be explored.

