The eCRFs are designed to prevent indeterminate responses; if any do occur, BCL will work with Fujifilm to resolve the issue. Regarding outliers the only continuous variable in the dataset is POM, a subjective ordinal variable for which each reader is permitted to use the full range on each case independent of values of other variables, such that no value of POM in 0 - 100% will be categorized as an outlier.

5. Results to be Reported

- Dates (timeline).
 - When cases were accrued on protocol FMSU2013-004A.
 - When cases were selected for the reader study.
 - When the readers' interpretations occurred.
 - When lesion matching occurred.
- *Clinical and demographic characteristics of cases.* For example: age, race, ethnicity, breast composition (BI-RADS breast density categories), study center, reference standard status (cancer, benign, recall, normal); and for cancers lesion type (mass, asymmetry, calcification, architectural distortion, other, or combinations thereof) and size (as determined on protocol FMSU2013-004A).
- *Clinical and demographic characteristics of readers*. For example: years in practice, whether the reader had specialized mammography training, number of mammograms read in the past year, percent of current practice that is mammography, usual hours spent in a clinical day (to address issues of reading fatigue), and whether or not they use C-View.
- *Flow diagram*. Reasons for any exclusions (for example, protocol deviations). If exclusions are minimal, this diagram may be omitted and replaced by text.
- Summaries and cross-tabulations.
 - Table of number of findings by reference standard status and modality for each study reader.
 - Means and SDs, and/or medians and quartiles or ranges, of POM requiring correct lesion localization by reference standard status and modality for each study reader.
 - Table of BI-RADS requiring correct lesion localization by reference standard status and modality for each study reader.
 - Table of recall requiring correct lesion localization by reference standard status and modality for each study reader.
- *AUC (primary endpoint).*
 - Graphs of the readers' non-parametric (trapezoidal) ROC curves based on per-subject POM scores requiring correct lesion localization for each review condition (FFDM read, DBT plus S-View read).

- Table of corresponding AUCs for FFDM, DBT plus S-View, and the pairwise differences between them.

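### Does scoring localised cancers on finding-level items and marked non-cancers on the overall item undermine the AUC and specificity comparison?

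*SAP*

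**What the plan says.** For a read with at least one marked finding, SAP 4.4 Table 1 takes the per-subject score from different form items according to truth.

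- **Non-cancer:** "POM: Overall POM recorded by the reader for the case" and "BI-RADS: Overall BI-RADS category recorded by the reader for the case. From Overall Patient Recall form page".
- **Cancer with a mark on a proven malignancy:** the highest POM among the matching marks, and "BI-RADS: Highest BI-RADS category recorded by the reader for any of these matched findings".
- **Cancer with marks that all miss:** BI-RADS 1 and the lowest POM that the rule allows.

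Footnote 2 to Table 1 says that each subject needs one score, "conditional on whether the subject does or does not have proven malignancies". Protocol 12.3.1 and Table 6 give the same rule; for non-cancers with findings, "the overall BI-RADS category recorded by the reader for the case will be used". On the reader form (SAP Appendix 1) the finding-level scores are items 11–12, 20–21 and 29–30. The overall BI-RADS and POM are items 32–33.

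SAP 3.4 states that "consistency of BI-RADS scores, POM scores, and recall decisions will not be forced"; its example is POM against BI-RADS for a single finding. Under SAP 4.11 the statistician will "verify that data values fall in allowable ranges and follow logical flow", with no mention of finding against overall scores. SAP 5 lists a "Table of BI-RADS requiring correct lesion localization by reference standard status and modality for each study reader" and a matching POM summary, both on the derived score.

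Protocol 12.3.3 defines false positives and true negatives by the per-subject BI-RADS score, then explains them in terms of individual findings. SAP 4.4 keeps only the definitions, and SAP 1 says the SAP prevails in a conflict.

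**The concern.** An ROC curve normally compares one measurement between diseased and non-diseased cases. Here, among marked reads, the measurement itself depends on disease status. If a reader gives a finding BI-RADS 4 and the case overall BI-RADS 3, the read is correct whichever way the truth falls; the opposite pattern is wrong either way. Nothing in the plan forces the two items to agree, and no planned table would show how often they do not.

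The primary AUC comparison (H1) and the specificity comparison (H6) would be at stake if readers disagreed with themselves more often in one modality. The within-modality AUC and specificity could also sit higher or lower than under a single-item rule. Sensitivity takes only finding-level scores for localised cancers, and recall comes from a separate yes/no question.

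**Working it through.** **1. What disagreement does to BI-RADS classification (marked reads)**

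| Best finding (matched, if cancer) | Overall | Localised cancer | Non-cancer |
|---|---|---|---|
| 4–5 | 4–5 | true positive | false positive |
| 4–5 | 1–3 | true positive | true negative |
| 1–3 | 4–5 | false negative | false positive |
| 1–3 | 1–3 | false negative | true negative |

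The second row flatters accuracy and the third harms it, so the net direction is unknown. Reads without findings are unaffected.

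**2. The plan's own precision**

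Inputs from SAP 4.10: 60 cancers, 240 non-cancers, R = 18, σ²ab = 0.0004, σ²w = 0.0001, r1 = 0.53, r2 − r3 = 0.02, margin 0.05, t with 17 df. The SAP names a binormal approximation for σ²c without printing it. The usual form was assumed, averaged over AUC 0.80 and 0.75, which gives about 0.00148.

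- Variance of the difference = (2/18) × {0.0004 + 0.0001 + 0.00148 × [1 − 0.53 + 17 × 0.02]} ≈ 0.000189; SD ≈ 0.01375.
- Power = 92.9%, against 92% stated (rounded down). Other reasonable readings of the inputs give 91.6% to 93.6%, so the plan's figure reproduces.
- CI half-width ≈ 2.11 × 0.01375 = 0.029. With equal AUCs the expected lower limit is about −0.029, which leaves 0.021 to the margin.

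**3. Scale for specificity**

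- Non-cancer reads per modality: 240 × 18 = 4,320. One point is 43.2 reads; the H6 margin of 0.05 is 216 reads.
- If exactly the benign and recall cases are marked, (48 + 72) × 18 = 2,160 reads. Then 43.2/2,160 = 2.0% and 216/2,160 = 10.0% of marked reads.
- With an assumed 30% marked (1,296 reads) these become 3.3% and 16.7%; with 70% (3,024 reads), 1.4% and 7.1%.

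The specificity difference moves only if net disagreement across the BI-RADS 4 cut differs between modalities.

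**4. Scale for AUC**

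For one reader, the change in empirical AUC equals the share of non-cancer reads rescored times the mean share of cancers that they pass (ties counted half). Assumed ranges: net modality gap 2–5 points among marked reads, 30–70% marked, 10–30% of cancers passed.

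- Smallest: 0.02 × 0.30 × 0.10 = 0.0006.
- Middle: 0.05 × 0.50 × 0.30 = 0.0075.
- Largest: 0.05 × 0.70 × 0.30 = 0.0105.
- Gap needed to use up the 0.021 at the upper assumptions: 0.021/(0.70 × 0.30) = 10 points.
- Gap needed to move the whole margin: 0.05/(0.70 × 0.30) = 24 points.

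The last two figures hold only under the 70% and 30% caps. There is also a second route: with equal disagreement in both modalities, the difference still moves if the share of cancers passed differs. For example, with 2.5% of non-cancer reads rescored in each modality, 0.025 × (0.30 − 0.10) = 0.005.

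**5. Would a rescored analysis settle it?**

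The natural check gives each marked non-cancer its highest finding score. That is a maximum over up to three findings, while cancers keep the maximum over matched findings only. The non-cancer maximum can only rise as more findings are marked, and the number marked may differ by modality. If the result diverged, one could not tell item disagreement from finding count. In cancers, an overall score above the matched finding may simply reflect another, unmatched finding.

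**The case for a change.** The best case for a change is that identical rules do not guarantee identical effects. FFDM shows one image per view and the other arm a slice stack plus S-View, so readers may mark and summarise differently. SAP 4.6.2 treats specificity with its confidence interval as part of a complete account of the device, and within-modality levels can move even when disagreement is equal. In an illustrative simulation (FFDM AUC 0.80, 30–50% of non-cancer reads marked, 10–50% of those with overall POM 10–20 points below the finding), using the overall item raised the within-modality AUC by 0.003 to 0.047. An unfavourable modality gap of 0.01 in AUC would cut power from 92.4% to 77.6% (using the unrounded σ²ab = 0.000432). A favourable gap would make non-inferiority easier to show. The check needs no new data and is most credible if fixed before analysis.

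What stands is that the reporting gap is real and the documents do not exclude unequal disagreement. What does not follow is that the plan is biased. Those sizes rest on assumed disagreement, and the power figure also on an assumed modality gap. The overall item is asked straight after the findings, and the sentence on unforced consistency illustrates POM against BI-RADS, not finding against overall. Specificity based on the reader's case-level assessment is a well-defined quantity and a natural per-subject one. H6 receives more than negligible alpha only after H1 to H5 have all been rejected.

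**Conclusion.** The concern does not call for a change. Protocol and SAP agree on the rule, which is fixed in advance, applied alike to both modalities and stated to depend on truth status. The asymmetry is the price of requiring localisation: an overall score cannot be tied to a lesion, so cancers need finding-level scores, while non-cancers have nothing to match and take the reader's case-level score. That is a fair trade-off, and following the plan as written gives an interpretable comparison.

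The size of any effect cannot be found from the documents. Under the assumed ranges in step 4, the AUC difference moves by at most 0.0105, about half of the expected 0.021 to the margin; a larger gap or a different share of cancers passed would move it more. It would matter mainly if the lower limit fell close to −0.05. The obvious rescored analysis would be exploratory at best, for the reason in step 5.

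Analysts can cross-tabulate overall against highest finding-level scores in marked non-cancers by modality from items already collected, if anyone asks. The explanatory sentences in Protocol 12.3.3 are a clerical mismatch with Table 6; they do not alter the operative definition, and the SAP both omits them and takes precedence.
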